A.3. Utilizing the Systems Analysis and Improvement Approach (SAIA) is a methodology that addresses the current cervical cancer screening and referral system within the existing healthcare framework. Implementation science (IS) research utilizes strategies to adapt, implement, and optimize evidenced-based interventions to improve health outcomes (36). SAIA is based on systems engineering to improve implementation. This tool analyzes the existing care cascade, then maps the work flow process, designs and implements a workflow adaptation, assesses the impact, and repeats this cycle for continued iterative system and process improvement (1). This approach works within the existing health system to address barriers and bottlenecks in the cervical cancer screening cascade (1), without simply performing the screening as an external study team. The SAIA methodology has the benefit of being a generalizable intervention that can be adapted to many different disease models and settings, contributing to the longevity and sustainability of this intervention.

A.4. Budget impact analysis (BIA) of SAIA in collaboration with the DOH aims to improve screening by determining the affordability of this tool. With limited budgets for health care programs in many LMICs, budget impact analyses provide valuable information to guide policy changes that are fiscally responsible and have high potential health impacts. If the budget impact analysis shows a modest impact on the County budget, this argues for further expansion of this tool to other clinics, and potentially to other counties across Kenya.

B. INNOVATION

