B.1. First application of SAIA in the field of cervical cancer; one of a few IS approaches applied to cervical cancer. Community engagement (37), education (38, 39), combined cancer screening programs (40), and media interventions (41) have been used in SSA to improve cervical cancer screening. SAIA is an innovative tool for the healthcare setting, and has previously been trialed successfully in other settings for different healthcare indications. This application of SAIA in a randomized controlled trial is an essential step forward for the field of cervical cancer screening and addresses the need for integrating screening into existing healthcare systems (11). Successful completion of this research will demonstrate improved performance at a local level, while providing more generalizable data about the utility of SAIA to guide scale-up nationally and in other countries facing similar challenges with cervical cancer screening.

B.2. A BIA of SAIA has the potential to move the field forward. Understanding the budget impact on the DOH can support broader roll-out of this program in other counties in Kenya and other LMICs facing similar challenges to screening. BIAs move beyond cost-effectiveness to highlight how this approach will affect the budget from the perspective of the payer in the health care system. This BIA is an important and necessary step to scale-up this intervention.

C. APPROACH. C.1.Preliminary Studies

C.1.A. Leader in IS. The UW Department of Global Health is a leader in IS research, including 85 projects in 41 countries, involving 119 faculty (42). Implementation science spans departments and programs including the Health Alliance International, International Training and Education Center for Health, and the Kenya Research and Training Center. Implementation research is also supported by the Center for AIDS Research (CFAR) Implementation Science Scientific Working Group, and an Implementation Science Core is proposed in our 2017 competing renewal (priority score 19). This institutional experience and leadership will benefit the successful completion of this research and [name] training.

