Time-and-Motion Studies: Time-and-motion studies estimate the time involved in each step of SAIA. These will be estimated over a 2-week period at each intervention site. Multiple SAIA visits will be averaged to give the best estimate of time needed for the intervention. Any time that is for research purposes only, like consent processes, will be subtracted from the total time of the intervention. Multiple providers and clients will be observed to provide a good estimate of the time from clinic entry to clinic exit for a cervical cancer screening. We will not collect private identifiable information about individuals that we will be observing and we will not interact with FP clients or clinic staff while we are doing these observations. The micro-costing and time-and-motion studies will be used to calculate the average cost of a new cervical cancer screen.

Budget Impact Analysis: The budget impact analysis will include direct program costs from the perspective of the DOH, that are estimated from the micro-costing methods illustrated above. Both the 'top-down' approach using routine expense reports and the 'bottom-up' approach using micro-costing will be used to refine our analyses. Standard practices for economic evaluations in health (52) and guidelines from the Panel of Cost-Effectiveness in Health and Medicine (53) will be used where possible to produce results that are accurate and generalizable. A standard 3% discounting rate will be used, with sensitivity analyses that use no discounting and 5% rate. Further sensitivity analyses will be conducted to produce best estimates under varying scenarios.

[figure not shown]

Figure 5. Study Design.

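### The main budget impact result is discounted at 3%, so for costs beyond the first year it falls below the cash the County must find; undiscounted outlays should be primary

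*Combined protocol and SAP*

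**What the plan says.** Section E.4 (Procedures), under C.2.C, has a paragraph on the budget impact analysis. It sets the viewpoint: "The budget impact analysis will include direct program costs from the perspective of the DOH". It then takes its conventions from general economic evaluation, adding that "guidelines from the Panel of Cost-Effectiveness in Health and Medicine (53) will be used where possible". The discounting rule follows: "A standard 3% discounting rate will be used, with sensitivity analyses that use no discounting and 5% rate".

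Two earlier sections say what the analysis is for. Section B.2 sets it apart from cost-effectiveness: "BIAs move beyond cost-effectiveness to highlight how this approach will affect the budget from the perspective of the payer in the health care system". Section A.4 gives its use in a decision: "If the budget impact analysis shows a modest impact on the County budget, this argues for further expansion of this tool to other clinics".

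C.2.C also plans to collect start-up costs at the beginning and running costs during the intervention, and to estimate an average cost per new screen. No time horizon is given for the budget projection, and nothing says that costs will be reported year by year.

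**The concern.** Discounting puts costs that fall at different times on a common present-value footing, so that options can be compared. That is a cost-effectiveness task. A budget holder has a different question: how much money must be found in each fiscal year? A present value does not answer it, because every later outlay has been scaled down.

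The protocol draws this distinction itself in section B.2, then gives the budget question a present-value main analysis in section E.4. The resulting error has a known direction: the reported figure is too low, and more so for later years. It leans towards the modest-impact finding that section A.4 would use to support expansion. What is at stake is the main figure of Aim 3 as the County would read it.

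**Working it through.** The documents state no budget impact figure, annual cost or horizon, so there is no planned number to reproduce. The check is therefore present-value arithmetic under stated assumptions.

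**Inputs from the documents**
- Main rate: "A standard 3% discounting rate will be used" (E.4, C.2.C).
- Other rates: "with sensitivity analyses that use no discounting and 5% rate" (same place).
- Trial duration: 18 months with the requested 6-month extension (E.7).

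**Assumptions**
- Equal annual costs over a horizon of H years.
- Costs counted at the start of each year (t = 0 to H−1) or at the end (t = 1 to H).

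**Formula.** Shortfall in the total = 1 − (1/H) × Σ (1+r)^(−t).

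**Discount factors at 3%** for t = 0 to 5: 1.0000, 0.9709, 0.9426, 0.9151, 0.8885, 0.8626.

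**Worked cases at 3%**
- 3 years, start of year: (1.0000 + 0.9709 + 0.9426)/3 = 0.971, a shortfall of 2.9%.
- 3 years, end of year: (0.9709 + 0.9426 + 0.9151)/3 = 0.943, a shortfall of 5.7%.
- 5 years, start of year: 4.7171/5 = 0.943, a shortfall of 5.7%.
- 5 years, end of year: 4.5797/5 = 0.916, a shortfall of 8.4%.

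| Assumed horizon | Shortfall at 3% | Shortfall at 5% | Shortfall at 0% |
|---|---|---|---|
| 1 year | 0% to 2.9% | 0% to 4.8% | 0% |
| 2 years | 1.5% to 4.3% | 2.4% to 7.0% | 0% |
| 3 years | 2.9% to 5.7% | 4.7% to 9.2% | 0% |
| 5 years | 5.7% to 8.4% | 9.1% to 13.4% | 0% |

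Each range runs from start-of-year to end-of-year timing.

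**Trial window only.** Leave the first 12 months undiscounted and discount the last 6 months by one year: 1 − (1 + 0.5/1.03)/1.5 = 1 − 0.990 = about 1.0%.

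**Effect of start-up costs.** As an illustration, take 5 years with start-of-year costs, plus a start-up cost at time zero equal to one year's cost. The cash total is 6 units and discounting removes 5 − 4.7171 = 0.283. The shortfall is 0.283/6 = 4.7%, against 5.7% without the start-up cost. Front-loading shrinks the gap.

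**The case against.** The strongest reply is that the undiscounted run is already planned, so the County will have it and the dispute is over which of two results is called primary. The documents do not use the term base case. This is true, and it makes the change cheap. It does not remove the point, because the natural reading of the paragraph makes 3% the main analysis, and a budget holder should not have to look for the budget figure among sensitivity runs.

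A second reply is that the 3% rate may be meant for annualising start-up or durable items, or for the cost per screen. Both are legitimate uses. But the sentence stands in the budget impact paragraph, while the cost per screen belongs to the preceding one. If a narrower use was intended, the text needs to say so.

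A third reply concerns size, and much of it stands. A reader might infer that the budget is understated by 13.7% or even 21.6%. Those figures are 1 − 1/1.03^5 and 1 − 1/1.05^5: the shortfall on a single cost five years ahead, the second at a rate planned only for sensitivity analysis. They do not describe the total. With a one-year horizon and no discounting within the year, the shortfall is nil.

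A reader might also infer that discounting would tip the expansion decision. The documents do not support that: they give no threshold for a modest impact and no County budget against which to judge one. Only the direction is established.

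Finally, a reader might conclude that the 5% run has to go. It moves further from cash, but as a labelled sensitivity result it does little harm, and dropping it is a matter of preference.

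**Conclusion.** The concern holds in a limited form. The plan's stated purpose calls for cash outlays by budget year, but its main analysis is a present value. For costs beyond the first year, the main figure is therefore lower than what the County must fund. That direction is certain at any positive rate.

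The size is not certain. Over assumed horizons of 3 to 5 years with equal annual costs, the total at 3% falls short by about 3% to 8%. Over a single year or the trial window it is little or nothing, and start-up costs at time zero reduce it further. The unstated horizon is a linked gap, because neither the size of the shortfall nor yearly outlays can be worked out without it.

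The point is confined to the reporting of Aim 3. The randomised comparison in Aim 2 does not depend on it.

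**What to change.** Amend the budget impact paragraph in section E.4 (C.2.C) as follows:

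- State the time horizon of the projection.
- Make undiscounted outlays per fiscal year over that horizon the primary budget impact result, with start-up and recurrent costs on separate lines.
- Keep 3%, and 5% if wanted, as labelled sensitivity analyses.
- Say where else a rate applies, for example in annualising start-up and durable items or in the cost per screen.

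The cost is a few sentences and a decision on the horizon. The undiscounted run and the collection of start-up and ongoing costs are already planned, so no new data are needed.

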5. SAMPLE SIZE DETERMINATION

Aim 1: In 2016, there were an estimated 140 FP clinics in Mombasa County. We anticipate abstracting data from roughly 75% (N=105) of these FP clinics for this aim. The clinics would be randomly selected from across Mombasa County, stratified by clinic size, including both high-volume and low-volume facilities. This cascade would aim to provide more information from a larger selection of clinics than the preliminary review in C.1.E. For the correlates of screening analysis, we estimate needing a total sample of 1672 FP clients, with 49 (3%) women screened (Table 1). While we saw 1% of clients screened in our preliminary data, we anticipate that a higher proportion of women would be screened if we incorporate other registers being used by clinics. We anticipate being able to reach this number of clients in this study based on data from our preliminary study (with over 12,000 clients seen in 60 clinics in a 3-month period).

Table 1. Sample sizes for failure to screen correlates for individual and clinic-level characteristics.

	Correlate present in women not screened	Correlate present in women screened	Absolute risk difference	Total sample size*
Individual-level characteristics				
HIV-positive	60%	20%	0.4	376
	60%	40%	0.2	1672
Younger age	80%	50%	0.3	581
	60%	30%	0.3	717
Clinic-level characteristics				
Facility level 3-4	20%	60%	0.4	325
	40%	60%	0.2	1672
High staff:patient ratio	10%	50%	0.4	237
	20%	60%	0.4	325

*This is the sample size required to have 80% power at an alpha 0.05 with varying proportions of women with different characteristics between women not screened and women screened. A ratio of screened to not screened of 1:33 was assumed.

Aim 2: The FP HIV SAIA Trial preliminary results suggest that very little cervical cancer screening is performed or being documented in FP registers. Of these available data, the proportion of FP clients screened was 0.6%. Because this screening prevalence may not be representative, we have used a more liberal estimation of 8% prevalence of screening based on the 2014 DHIS estimates (the most recent resource available). FP clinics had an average of 183 clients in a 3-month period. Most clients follow-up every 3 months so this is a conservative estimate of total clients in a 12-month period. We will assume that following the intervention, 20% of women will be screened for cervical cancer. To calculate a sample size for a cluster RCT, the cluster size variability (κ) must be estimated with literature often citing $\kappa \leq 0.25$ and rarely exceeding 0.5 (54). We have estimated a κ of 0.5 to be conservative, which translates to an intra-class correlation coefficient of approximately 0.05. Cluster size variability of FP clinics was calculated as 0.74 using data in 1.C.E. With an $\alpha=0.05$, 10 clusters per arm will provide 90% power to detect a risk difference of 12% from the intervention.

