C.1.E. Preliminary data on cervical cancer screening in Mombasa County from the FP HIV SAIA trial show low screening and incomplete documentation. [name] has had discussions with key collaborators in Mombasa County including the Director of Health (see letter), noting that the majority of cervical cancer screening is conducted in either FP clinics or HIV clinics. The County's policy is that screening should be documented in the FP register. Cervical cancer screening is reported to the County for all clinics that receive County FP commodities. These data are compiled into the District Health Information System (DHIS). The quality of different data sources has not been formally evaluated. Preliminary results from the cervical cancer screening review linked to the FP HIV SAIA trial underscore the importance of the project proposed in the present application. The 60 clinics analyzed saw a mean of 204 FP clients per clinic (SD 172) during a 3-month period (a total of 12,236 clients over the three-month period of our data review). Of the 60 clinics, 4 (7%) did not record cervical cancer screening in the FP register, but reported recording it elsewhere. Because we did not review these alternative records in this initial survey, these clinics are excluded from subsequent analyses. Of the 56 remaining clinics, 7 (13%) recorded any cervical cancer screening. Only 120 women (1%) were screened. These preliminary data suggest few FP clinics perform cervical cancer screening, and that most women accessing FP services are probably not being screened for cervical cancer. Of the clinics offering screening, not all are documenting this activity in the FP register. Moving forward, data collected in outside logs could be entered into FP registers or abstracted separately. These preliminary data provide valuable information for this K08 proposal, which will comprehensively document screening practices in Mombasa County using all the available documentation sources. We will explore why screening prevalence and appropriate documentation is so low, and address this implementation gap with clinic-specific interventions using SAIA.

E. METHODOLOGY

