6. DATA MANAGEMENT

Aim 1:

Cervical cancer screening care cascade: The care cascade will examine the counts and proportions aggregated from the selected FP clinics as outlined in Figure 3. This cascade will account for appropriate exits from the cascade (e.g. outside screening age range, or screened negative) and losses in the cascade (e.g. not screened, or positive screen not referred for follow-up). Our research group has experience working with this type of complex care cascade in the setting of isoniazid prophylactic therapy for tuberculosis prevention, where there are multiple steps at which individuals can exit appropriately, be lost, or move on to the next step (55). We aim to model a cervical cancer screening care cascade in a similar manner.

Correlates of screening: Cervical cancer screening will be modeled as a binary outcome. Logistic regression will be used to examine correlates of screening including age, HIV status of clients, and specific clinic characteristics (detailed in Procedures). Analyses will be adjusted for any clustering by clinic.

Aim 2: The primary outcome is the proportion of all FP clients aged 21-65 years who were screened for cervical cancer over the total number of eligible clients. These outcomes will be assessed every 3 months in the 12-month study period. We are requesting an extension of the trial for an additional 6 months. Women who are not FP clients who are referred to a clinic solely for screening will be excluded as they could inflate the proportion of women screened. These women will be identified because they did not receive FP products or HIV testing and were only entered in the FP register because of screening. Generalized estimating equations with a binary link, clustered by clinic, will compare proportions screened in intervention versus control clinics longitudinally to account for correlation across time and between clinics. Interviews will be audio-recorded, transcribed, translated, coded for major themes, and analyzed using Dedoose software (56).

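### Table 1 leaves out clustering by clinic, so its 80% power claim fails for clinic-level correlates, most clearly for facility level at 40% versus 60%

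*Combined protocol and SAP*

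**What the plan says.** Section E.5 (Sample size determination), Aim 1, sets the need: "we estimate needing a total sample of 1672 FP clients, with 49 (3%) women screened". The footnote to Table 1 states "This is the sample size required to have 80% power at an alpha 0.05" and adds "A ratio of screened to not screened of 1:33 was assumed". Half of the table's eight rows are individual-level (HIV status, younger age) and half are clinic-level (facility level, staff:patient ratio). The figure of 1,672 comes from the two rows with a 20-point difference: HIV-positive at 60% versus 40%, and facility level at 40% versus 60%. The table and its text give no ICC, design effect or number of clients per clinic.

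On clinics, the same section says "We anticipate abstracting data from roughly 75% (N=105) of these FP clinics for this aim". Section E.6 (Data management), Aim 1, specifies logistic regression and says "Analyses will be adjusted for any clustering by clinic". The only allowance for clustering is in the Aim 2 calculation, which takes a between-cluster coefficient of variation k of 0.5, "which translates to an intra-class correlation coefficient of approximately 0.05".

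**The concern.** The sample size and the analysis do not match. The table counts clients as independent, while the model will widen standard errors for correlation within clinics. This matters most for a characteristic that is identical for every client of a clinic, because the information then lies mainly in the number of clinics. The preliminary data in C.1.E suggest that screening is concentrated: "Of the 56 remaining clinics, 7 (13%) recorded any cervical cancer screening".

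Hypothesis 1 predicts that failure to screen is associated with clinic-level factors as well as patient-level ones. If facility level or staffing shows no association, a reader who trusts the stated 80% power would take that as fair evidence of no sizeable association. The study may not support that reading.

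**Working it through.** **Inputs.** From E.5: power 80%, alpha 0.05 (two-sided assumed; sidedness is not stated), ratio r = 33, 105 clinics. From C.1.E: mean 204 clients per clinic in 3 months, SD 172, so the coefficient of variation (CV) of clinic size is 172/204 = 0.84. The Aim 2 text gives 0.74. An even spread of 1,672 clients over 105 clinics is assumed, so m = 1,672/105 = 15.9.

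**Reproducing the table (40% not screened, 60% screened).**
- Pooled proportion = (0.60 + 33 × 0.40)/34 = 0.406.
- Screened women needed = [1.960 × √((1 + 1/33) × 0.406 × 0.594) + 0.842 × √(0.24 + 0.24/33)]² / 0.20² = 48.7, rounded up to 49.
- Total = 49 × 34 = 1,666, against 1,672 stated.

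All eight rows reproduce within 3%. At its stated size each gives 80.3–80.5% power, so there is no clustering allowance and almost no reserve.

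**Range of ICC.** With k = 0.5 at the 3% screened assumed for Aim 1, ICC = 0.25 × 0.03/0.97 = 0.0077. The Aim 2 figure is 0.05. Values of 0.02 and 0.10 fill out the range.

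**Clinic-level row, 40% versus 60%, 1,672 clients.** Design effect (DE) = 1 + (m − 1) × ICC; effective N = 1,672/DE.

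| ICC | DE | Effective N | Power |
|---|---|---|---|
| 0.0077 | 1.11 | 1,500 | 76% |
| 0.02 | 1.30 | 1,288 | 70% |
| 0.05 | 1.75 | 958 | 57% |
| 0.10 | 2.49 | 671 | 43% |

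A simulation with 105 clinics of 16 clients and a cluster-robust test (4,000 runs) gave 74%, 68%, 55% and 43%, against 78% with almost no clustering.

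**Individual-level row, 60% versus 40%, 1,672 clients.** DE = 1 + (m − 1) × ICC of the correlate × ICC of screening. With both at 0.05, DE = 1 + 14.9 × 0.0025 = 1.04 and power is 79%. For correlate ICCs of 0.01–0.10 and screening ICCs of 0.02–0.10, DE is 1.00–1.15 and power 75–80%.

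**The other six rows.** They need 237 to 717 clients. If 1,672 are used, even a DE of 1.75 leaves about 91% to 99.9% power.

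**All clients abstracted.** 105 × 204 = 21,420, before the age limit. DE = 1 + ((1 + CV²) × 204 − 1) × ICC, for the clinic-level 40% versus 60% row:

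| ICC | Size CV | DE | Effective N | Power |
|---|---|---|---|---|
| 0.02 | 0 | 5.06 | 4,233 | 99% |
| 0.02 | 0.84 | 7.94 | 2,698 | 95% |
| 0.05 | 0 | 11.15 | 1,921 | 86% |
| 0.05 | 0.74 | 16.74 | 1,280 | 69% |
| 0.05 | 0.84 | 18.35 | 1,167 | 65% |

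**Ceiling.** However many clients each clinic supplies, effective N cannot exceed 105/ICC with equal sizes. It stays below 1,672 once the ICC exceeds 105/1,672 = 0.063. As a rough guide, if one clinic in eight did all the screening at equal rates, k² = 7, and at 1% screened ICC = 7 × 0.01/0.99 = 0.07.

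**The case against.** The strongest reply is that 1,672 is a minimum and not the planned sample. The Aim 1 procedures take every client aged 21–65 seen in a 3-month window, and E.5 points to more than 12,000 clients in 60 clinics. This stands. A reader might infer that the correlates analysis is bound to be underpowered, but the documents do not support that: at an ICC of 0.02 or less, full abstraction gives about 95% or more. It is not a complete answer, because at ICC 0.05 the result turns on clinic-size variation, and above about 0.063 extra clients cannot help.

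A second reply is that 0.05 belongs to Aim 2, where more women are expected to be screened. This also stands, and it is why a range is shown. At 0.0077 the loss at 1,672 clients is only about 4 points.

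A third reply is that the table contains no calculation error, that the clustering adjustment still addresses the standard errors, and that the randomised comparison has its own clustering allowance. All true. The fault is an omitted assumption in an observational analysis, and it affects the stated power.

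Three stronger readings are tempting and should be resisted:
- That all of Table 1 fails. Individual-level correlates lose little, and the rows with larger differences keep more than 80% if 1,672 clients are used.
- That multiplying 1,672 by 1.75 to get 2,920 clients cures the problem. That holds only at 15.9 clients per clinic, which takes about 183 clinics, and E.5 counts 140 in the county. Over 105 clinics, 2,920 clients is 27.8 each, DE is 2.34, effective N is 1,248 and power is 68%.
- That the 7-in-56 figure reduces the analysis to about 13 screening clinics against 92 others. That figure comes from family planning registers alone over 3 months. Aim 1 adds other logs and 12 months of follow-up, and the planned model is a client-level regression, not a comparison of two groups of clinics.

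**Conclusion.** The point holds for the clinic-level rows of Table 1. Their sizes come from a formula for independent clients and do not deliver the stated 80% power once clustering is taken into account, at virtually any positive ICC. The material case is facility level at 40% versus 60%, where 1,672 clients give between 76% and 43% power for ICCs from 0.0077 to 0.10. Whether the study as carried out will fall short is open. It depends on the Aim 1 ICC and on the number and spread of clients abstracted, and the plan does not give the ICC.

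These figures assume a two-sided test and, at 1,672 clients, an even spread over 105 clinics. The full-abstraction figures assume the 3-month mean of 204 clients carries over to those clinics; the age limit would lower it. The correction is worth making, but it does not touch the trial's primary comparison.

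**What to change.** In E.5, restate the clinic-level rows of Table 1 with a design effect. Use 105 clinics, the clients per clinic actually to be abstracted after the age limit, a size CV of 0.74 to 0.84, and a stated ICC range such as 0.0077 to 0.10. Report effective sample size and power for each row, and say plainly where 80% for a 20-point difference is not reached, so that null clinic-level results are not read as adequately powered. For individual-level rows, a sentence saying that the loss is small and depends on how far the correlate itself clusters by clinic is enough.

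If a client target is wanted for facility level at 40% versus 60%, solve N / (1 + (N/105 − 1) × ICC) = 1,672. At ICC 0.05 and equal clinic sizes this gives about 7,800 clients. Above an ICC of about 0.063 no client target exists for 105 clinics, and the text should say so.

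The cost is a revised table and a few sentences. No data collection changes, because the planned abstraction is already larger than 1,672.

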C.1.D. Adaptations of SAIA methods in ongoing trial, led by [name]. Adaptations of SAIA methods are currently being used to address linkage of HIV services in the ongoing trial “RCT of an implementation science tool to integrate HIV testing into family planning services” (K24 HD088229-01; PI, [name]; FP HIV SAIA Trial) with [name] (primary mentor) and [name] (co-mentor). To meet the national guideline that all women should be tested for HIV when accessing FP services (48), a data entry template for recording of HIV counseling and testing was integrated into the Kenyan FP registers in 2008. Our UW group is addressing this guideline in the FP HIV SAIA trial that compares SAIA to usual procedures to improve HIV testing at FP clinics in Mombasa County. A preliminary performance review of 60 FP clinics in Mombasa County collected data from FP registers and clinic manager interviews. Of 60 clinics, a total of 4389 new FP clients were seen in a 3-month period (mean of 73 new clients per clinic (standard deviation [SD] 81)). Only 23 clinics reported any HIV testing, with a total of 420 new FP clients screened in a 3-month period. Three of these clinics performed the majority of screening (302 screens, 72%). As a Senior Fellow in Infectious Diseases, [name] has led the implementation for this project. She prepared the applications for ethical and humans subjects approval in the US and Kenya, developed data collection tools, trained study staff, created the database, launched the study, and coordinated planning, logistics, and dissemination of findings with Mombasa County. This study has provided [name] with valuable experience in implementing SAIA, and demonstrates the great potential for additional implementation research in Mombasa.

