2. STUDY POPULATION

There will be three different groups of subjects in this research proposal:

1. Individual FP clients' data will be abstracted from FP registers. However, there will be no contact with individual FP clients by study staff.
2. Family planning clinics as a unit to be randomized. Study staff will work with clinic staff for both data abstraction and during the intervention if randomized to this arm of the trial. In addition, micro-costing and time-and-motion studies will be conducted in FP clinics for the SAIA budget impact analysis.
3. Family planning clinic managers and staff.

Inclusion Criteria:

Family planning clinics

Sampling plan: A selection of 20 FP clinics will be selected to be randomized to SAIA versus usual procedures. The FP clinics will receive County-supplied FP products, which generally means they are reporting their activities to the County, including cervical cancer screening. Clinics will be spread out throughout the 5 sub-Counties in Mombasa.

Eligibility: All FP clinics that receive County-supplied FP products will be eligible to participate.

FP clinic managers and staff

Sampling plan: A selection of FP clinic managers and staff will be approached to answer questions about their respective FP clinics in a semi-structured interview. To understand the implementation of cervical cancer screening in the CFIR framework, in-depth interviews will also be conducted with a random sampling of FP clinic managers.

Eligibility: Any FP clinic manager that is 18 years and older is eligible to be interviewed. These clinic managers can be male or female.

FP client data abstraction: Family planning client data will be abstracted from included FP clinics for female FP clients who access FP clinics during our data collection windows. We anticipate including all female FP clients.

Exclusion Criteria

Family planning clinics

Any clinic that is expected to be closed during part or all of the SAIA intervention period will be excluded. Any FP clinic that was previously included in the FP HIV SAIA trial will be excluded.

FP clinic managers and staff

No exclusion criteria

FP client data abstraction: No exclusion criteria.

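### Does the mislabelled κ, and the silence on how the clinic-size variation of 0.74 was used, undermine the 90% power for Aim 2?

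*Combined protocol and SAP*

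**What the plan says.** Section E.5 (Aim 2) opens with "To calculate a sample size for a cluster RCT, the cluster size variability (κ) must be estimated". It then states "We have estimated a κ of 0.5 to be conservative, which translates to an intra-class correlation coefficient of approximately 0.05", and directly afterwards "Cluster size variability of FP clinics was calculated as 0.74 using data in 1.C.E". The clinic size is given as "FP clinics had an average of 183 clients in a 3-month period", which the plan treats as a cautious count for 12 months. With 8% screened under usual procedures and 20% under the intervention, it concludes that "10 clusters per arm will provide 90% power to detect a risk difference of 12% from the intervention".

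The preliminary data are in two places. C.1.E reports "The 60 clinics analyzed saw a mean of 204 FP clients per clinic (SD 172) during a 3-month period". It then says that 4 of the 60 clinics recorded screening outside the register and are left out of later analyses, so 56 remain. C.1.D reports a "mean of 73 new clients per clinic (standard deviation [SD] 81").

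E.6 names generalized estimating equations (GEE) clustered by clinic, intended to account for correlation over time and between clinics. It names no working correlation. E.11 says that 60 new clients per clinic would still give at least 80% power.

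**The concern.** Three things look wrong.

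- **Label.** One label covers two different quantities, 0.5 and 0.74. A reader who took the larger figure as κ would conclude that the trial is badly underpowered.
- **Sources.** The inputs do not match the section cited for them. C.1.E gives 172/204 = 0.84 rather than 0.74, and 204 clients rather than 183. E.11 cites C.1.E for 60 new clients, but that section prints no count of new clients, and C.1.D prints 73.
- **Use of 0.74.** The plan does not say whether the clinic-size variation entered the power. Unequal clinics cost little under one weighting and a good deal under another, and E.6 does not name the weighting.

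If the 90% held only for equal clinics, the case for 20 clinics would be weaker than stated. So would the fallbacks in E.11 (new clients only, or analysis by HIV status).

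**Working it through.** **Inputs.** From E.5: p0 = 0.08, p1 = 0.20, difference 0.12, c = 10 clinics per arm, m = 183, κ = 0.5, α = 0.05 (taken as two-sided), clinic-size CV 0.74. From E.11: m = 60.

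**1. Which quantity is κ?** If κ is the between-clinic CV of screening proportions, then

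ICC = κ²(p0² + p1²) / [p0(1−p0) + p1(1−p1)] = 0.25 × 0.0464 / 0.2336 = 0.0497.

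This is the plan's 0.05. A CV of clinic size has no such conversion, so the calculation used the right quantity under the wrong name.

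**2. The stated 90%, equal clinics.** The variance of the difference is

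[0.2336/183 + 0.25 × 0.0464]/10 = (0.00128 + 0.01160)/10 = 0.001288, so SE = 0.0359 and 0.12/0.0359 = 3.34.

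Power is Φ(3.34 − 1.96) = 91.7%. With t on 18 df it is 88.5%. With the usual one-cluster correction (c − 1 = 9 in place of 10) it is 88.7%. All are within two points of 90%.

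**3. Adding clinic-size CV 0.74, ICC 0.05.**

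- *Near-optimal weighting (exchangeable type).* The equal-size design effect is 1 + 182 × 0.05 = 10.1. With λ = 183 × 0.05/10.1 = 0.906, it becomes 10.1/[1 − 0.74² × 0.906 × 0.094] = 10.6.
- *Every client weighted equally (independence type).* The design effect is 1 + [(1 + 0.74²) × 183 − 1] × 0.05 = 15.1.

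| Weighting at CV 0.74 | Effective n per arm (1,830 / design effect) | Power, normal | Power, t 18 df | Simulated |
|---|---|---|---|---|
| Near-optimal | 172.7 | 90.4% | 87.0% | 87–88% |
| Equal client weights | 121.1 | 78.0% | 73.4% | 78–80% |

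The simulation used beta-binomial data, 20,000 runs and t on 18 df. The size CV realised with 10 clinics was 0.62 to 0.66, below the nominal 0.74. So the 90% fits equal clinics, and it also fits 0.74 being included under efficient weighting.

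**4. The E.11 fallback, m = 60.** Equal clinics: variance (0.00389 + 0.01160)/10, ratio 3.05, power 86.2% (82.2% with t; 82.4% with the one-cluster correction). The claim of at least 80% reproduces. At CV 0.74 with near-optimal weighting it is 82.7% (78.4% with t). Sixty is a 3-month count, so a year's intake would be larger.

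**5. Can 183, 0.74 and 60 come from the 56 clinics?**

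- All clients: 12,236 − 56 × 183 = 1,988, so the 4 excluded clinics would average 497.
- New clients: 4,389 − 56 × 60 = 1,029, so they would average about 257.
- Spread: an SD of 0.74 × 183 = 135 in the 56 clinics agrees with the printed SD of 172 for all 60 if the 4 clinics have an SD of about 310 to 350, depending on the divisor.

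This is feasible. Leaving out a few large clinics also moves all three figures in the direction seen: 204 to 183, 0.84 to 0.74, and 73 to 60.

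**The case for a change.** The strongest contrary case is about weighting. E.6 defines the outcome as screened clients over all eligible clients, pooled. That is compatible with equal client weights, and GEE under an independence working correlation with robust errors would give them. At CV 0.74 this choice alone moves power by about 12 to 14 points in closed form, or 8 to 9 in simulation. It also shifts the estimate between a client average and a clinic average when screening depends on clinic size. Balancing the arms on clinic size does not remove size variation within arms.

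That sensitivity is real, and so are the wrong label and the loose citation. But the plan does not say it will use independence weights, and its stated aim of accounting for correlation points an analyst, without binding one, to an exchangeable-type structure. Under that structure power stays close to 90%. The lower figures also describe a single cross-sectional comparison. They give no credit for restricted randomisation, baseline data or repeated quarterly outcomes, any of which could raise power.

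Two further arguments fail. Entering 0.74 as κ gives 60% to 64%, but the plan fixes κ at 0.5 and attaches 0.74 to the clinics. Pairing 60 new clients with 81/73 = 1.11 combines a mean and a CV that probably come from different sets of clinics.

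**Conclusion.** No change follows. Both power claims reproduce: 88.5% to 91.7% against the stated 90%, and 82% to 86% with equal clinics against at least 80%. With clinic-size CV 0.74 and near-optimal weighting, the main figure is about 90% (normal) or 87% (t). The label on κ is a clerical slip that did not reach the calculation. The differences from C.1.D and C.1.E have a plausible source in the 56-clinic subset, although the plan does not confirm it. The working correlation is a detail that analysts would ordinarily settle. Settling it in writing would need no extra clinics and would alter no conclusion.

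This rests on taking κ = 0.5 as the plan does; whether 0.5 is large enough is a separate question. It also assumes that the trial clinics vary in size as the preliminary ones did, although E.2 states "Any FP clinic that was previously included in the FP HIV SAIA trial will be excluded". Were every client weighted equally, power would be about 73% to 80%.
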